4.4.1 Clinical Criteria for Early Study Termination

There are no prespecified criteria for terminating the study early.

5 STUDY POPULATION

As stated in the Code of Conduct for Clinical Trials (Appendix 1.1), this study includes participants of varying age (as applicable), race, ethnicity, and sex (as applicable). The collection and use of these demographic data will follow all local laws and participant confidentiality guidelines while supporting the study of the disease, its related factors, and the IMP under investigation.

Prospective approval of protocol deviations to recruitment and enrollment criteria, also known as protocol waivers or exemptions, is not permitted.

5.1 Inclusion Criteria

An individual is eligible for inclusion in the study if the individual meets all of the following criteria:

Type of Participant and Disease Characteristics

1. Has a diagnosis of NT1, including a valid PSG within the previous 5 years and a current diagnosis of NT1 for at least 6 months based on criteria established by the International Classification of Sleep Disorders- Third Edition. A current NT1 diagnosis based on the Diagnostic and Statistical Manual of Mental Disorders, Fifth Edition (DSM-5) [American Psychiatric Association 2013] is also acceptable.

Note: At the discretion of the investigator, a valid PSG within the past 10 years may be acceptable. Alternatively:

A PSG including MSLT can be repeated at the site during the Screening period or, A CSF hypocretin A level < 110 pg/ml is also acceptable as confirmatory of a NT1 diagnosis in the absence of valid PSG data. If not available, a CSF sample can be collected for hypocretin A level assessment at the discretion of the investigator.

2. Is positive for HLA-DQB1*06:02 allele supporting a diagnosis of NT1

Note: At the discretion of the investigator, participants with a negative HLA-DQB1*06:02 genotyping, but a PSG and/or a CSF hypocretin A level (per IC#1) supporting a diagnosis of NT1 may be enrolled in the study.

3. Has a baseline history of unequivocal cataplexy prior to initiation of anti-cataplexy medications.
4. Is free of any disease that in the opinion of the investigator would interfere with trial evaluations based on medical history, physical and targeted neurological examinations, VS measurements and ECG performed prior to enrollment (abnormal VSs and ECGs may be repeated once to confirm eligibility). Subjects with chronic medical conditions including but not limited to hyperlipidemia, and hypothyroidism which have been well-controlled on a stable dose of medication for the past two months, may be enrolled if clinically acceptable to the investigator and the Sponsor.

5. Has a BMI between 18 and 32 kg/m², inclusive. See Section 8.3.3 for criteria on rounding to the nearest whole number. BMI = weight (kg)/height (m)².

Note: Participants who have a BMI up to 35.0 kg/m² may be enrolled at the discretion of the investigator.

Demographics

6. Is an individual of any sex/gender, from 18 years to 55 years of age inclusive, at the time of providing the informed consent.

Assigned Male Sex at Birth

7. If capable of producing sperm, the participant agrees to the following during the intervention period and for at least the time needed to eliminate the study intervention after the last dose of study intervention. The length of time required to continue contraception for the study intervention is:

- cci

Abstains from penile-vaginal intercourse as their preferred and usual lifestyle (abstinent on a long-term and persistent basis) and agrees to remain abstinent

OR

Uses contraception as detailed below unless confirmed to be azoospermic (vasectomized or secondary to medical cause, documented from the site personnel's review of the participant's medical records, medical examination, or medical history interview) as detailed below:

- Uses a penile/external condom when having penile-vaginal intercourse with a nonparticipant of childbearing potential who is not currently pregnant and should also be advised of the benefit for that partner to use an additional method of contraception, as a condom may break or leak.

Note: Participants capable of producing ejaculate whose partner is pregnant or breastfeeding must agree to use penile/external condom during each episode of sexual activity in which the partner is at risk of drug exposure via ejaculate.

- Contraceptive use by participants capable of producing sperm should be consistent with local regulations regarding the methods of contraception for those participating in clinical studies. If the contraception requirements in the local label for any of the study interventions are more stringent than the requirements above, the local label requirements are to be followed.

Assigned Female Sex at Birth

8. A participant assigned female sex at birth is eligible to participate if not pregnant or breastfeeding, and at least one of the following conditions applies:

- Is not a POCBP

OR

- Is a POCBP and must meet all the bullet points below:
 - Uses a contraceptive method that is highly effective (with a failure rate of <1% per year), or is abstinent from penile-vaginal intercourse as their preferred and usual lifestyle (abstinent on a long-term and persistent basis), as described in Appendix 5 during the intervention period and for at least 7 days after the last dose of study intervention. The investigator should evaluate the potential for contraceptive method failure (ie, noncompliance, recently initiated) in relationship to the first dose of study intervention. Contraceptive use by POCBPs should be consistent with local regulations regarding the methods of contraception for those participating in clinical studies. If the contraception requirements in the local label for any of the study interventions are more stringent than the requirements above, the local label requirements are to be followed.
 - Has a negative highly sensitive pregnancy test (urine or serum) as required by local regulations within 24 hours (for a urine test) or 72 hours (for a serum test) before the first dose of study intervention. If a urine test cannot be confirmed as negative (eg, an ambiguous result), a serum pregnancy test is required. In such cases, the participant must be excluded from participation if the serum pregnancy result is positive. Additional requirements for pregnancy testing during and after study intervention are in Section 8.3.7.
 - Medical history, menstrual history, and recent sexual activity has been reviewed by the investigator to decrease the risk for inclusion of a POCBP with an early undetected pregnancy.

Informed Consent

9. The participant (or legally acceptable representative) has provided documented informed consent for the study. The participant may also provide consent/assent for FBR. However, the participant may participate in the study without participating in FBR.

Additional Categories

10. Is willing to forego operating a motor vehicle or heavy machinery from the EDS SOC washout period through Part 1 and Part 2 and until reinitiation of EDS SOC after completion of all study procedures in the last treatment period of Part 2.
11. Reports a total sleep time of > 6 hours on at least 4 out of 7 nights each week within the 4 weeks prior to screening visit.
12. Has regular sleep initiation times no later than midnight.
13. Agrees not to engage in night shift work, and not to cross more 3 times zones during the 2 weeks prior to randomization and throughout the course of the study.
14. Willing to comply with the study restrictions (see Section 5.3 for a complete summary of study restrictions).

5.2 Exclusion Criteria

An individual must be excluded from the study if the individual meets any of the following criteria:

Medical Conditions

1. History of or current hypertension defined as a SBP ≥ 140 mm Hg and a DBP ≥ 90 mm Hg.
2. Has underlying cardiovascular or cerebrovascular conditions in which an acute rise in blood pressure would pose a clinical concern, including but not limited to aneurysms or arteriovenous malformations.
3. Has a history of renal or hepatic impairment.
4. Has screening safety laboratory findings consistent with moderate or severe hepatic impairment, including but not limited to clinically significant elevations in AST, ALT, alkaline phosphatase, or bilirubin above normal range; clinically significant decreases in albumin below normal range; clinical significant decreases in platelet count below normal range.
5. Has an estimated eGFR ≤ 80 mL/min/1.73 m² based on the 2021 CKD-EPI.

CKD-EPI Equation:

$$\text{eGFR}_{\text{Cr}} = 142 \times \min(\text{Scr}/K, 1)^{\alpha} \times \max(\text{Scr}/K, 1)^{-1.200} \times 0.994^{\text{Age}} \times 1.012 [\text{if female}]$$

Where Scr is serum creatinine, K is 0.7 for females and 0.9 for males, α is -0.241 for females and -0.302 for males, min indicates the minimum of Scr/K or 1, max indicates the maximum of Scr/K or 1

Participants who have an eGFR of up to 10% below 80 mL/min/1.73 m² may be enrolled in the study at the discretion of the investigator.

6. Has a history of cardiac ischemia or cerebral ischemia including but not limited to history of stroke, transient ischemic attack, or transient global amnesia.
7. Based on clinical interview and responses on the C-SSRS, is at imminent risk of self-harm or of harm to others in the opinion of the investigator. Participants must be excluded if they report suicidal ideation with intent, with or without a plan or method (eg, positive response to item 4 or 5 in assessment of suicidal ideation on the C-SSRS) in the *past 5 years* or suicidal behavior in *their lifetime*.
8. Mentally or legally incapacitated, has significant emotional problems at the time of prestudy (screening) visit or expected during the conduct of the study or has a history of clinically significant psychiatric disorder of the last 5 years. Participants who have had situational depression may be enrolled in the study at the discretion of the investigator.
9. History of cancer (malignancy). Participants with definitively treated disease who, in the opinion of the study investigator, are highly unlikely to have a recurrence for the duration of the study may be enrolled at the discretion of the investigator.

10. Has a history of any of the following sleep disorders:
 - obstructive sleep apnea (OSA) defined as an Apnea Hypopnea Index > 15 per hour per the AASM alternate criteria,
 - primary insomnia (within the past 6 months),
 - circadian rhythm sleep disorder,
 - shift work sleep disorder (within the past 6 months),
 - clinically significant parasomnia at the discretion of the investigator.
11. Has a medical condition that in the opinion of the investigator, may account for the patient's excessive daytime sleepiness, e.g., pain, cardiac disease, nocturia (>3 times/night), or hot flashes.
12. For participants requiring lumbar puncture to determine study eligibility: Has a medical condition that in the opinion of the investigator may increase the risks associated with a lumbar puncture (eg, individuals with increased intracranial pressure, bleeding diathesis).
13. Has a history of seizure disorder, clinically significant head trauma, or past invasive intracranial surgery or clinically significant dementia.
14. Participants has, in the opinion of the investigator, a confounding psychiatric disorder such as any history of a psychotic disorder (e.g. schizophrenia, schizoaffective disorder, delusional disorder, bipolar disorder) or currently has active, inadequately-treated depression, post-traumatic stress disorder, or other anxiety disorder.
15. History of significant multiple and/or severe allergies (eg, food, drug, latex allergy), or has had an anaphylactic reaction or significant intolerability (ie, systemic allergic reaction) to prescription or nonprescription drugs or food.
16. Positive test(s) for HBsAg, hepatitis C antibodies or HIV. Note: Participants with a documented cure and/or a positive serologic test for HCV with a negative HCV viral load may be included upon consultation with the Sponsor.
17. The participant had a major surgery and/or donated or lost 1 unit of blood (approximately 500 mL) within 4 weeks prior to the prestudy (screening) visit.
18. Participants, in the opinion of the investigator, has a history or current evidence of any condition, therapy, lab abnormality or other circumstances that might confound the results of the study, or interfere with the patient's participation for the full duration of the study, such that it is not in the best interest of the patient to participate.

Prior/Concomitant Therapy

19. Unable to refrain from or anticipates the use of CYP3A4 inhibitor and/or inducer drugs and food, drug, supplements or other products with known stimulating or sedating properties beginning ~ 2 weeks (or 5 half-lives) prior to administration of the first dose of the study intervention, throughout the study (including washout intervals between treatment periods and study parts), and until the poststudy visit: TCAs, amphetamine, hypnotics, tranquilizers, sedating antihistamines, benzodiazepines, anticonvulsants, clonidine, pemoline, melatonin, guarana, ma huang, kava-kava, valerian, hoodia, St. Johns wort and any other stimulants and alerting agents prescribed for use on a daily basis. There may be certain medications that are permitted (see Section 6.5).

Prior/Concurrent Clinical Study Experience

20. Participated in another investigational study within 4 weeks (or 5 half-lives, whichever is greater) prior to the prestudy (screening) visit. The window will be derived from the date of the last visit in the previous study.

Diagnostic Assessments

21. QTc interval ≥ 450 msec.

Other Exclusions

22. Is under the age of legal consent.
23. Has a history of substance abuse or dependence within the past two years (except if currently in sustained full remission for at least one year or meets criteria for early full remission, according to DSM-IV-TR). Substances include alcohol, hypnotics, cannabis, nicotine (only if the nicotine dependence is affecting sleep) and any illicit drugs of abuse. Participants must have a negative drug screen prior to randomization.
24. Consumes the equivalent of more than 10 cigarettes a day or routinely smokes during the night.
25. Has history of tobacco use associated with maintaining wakefulness (i.e., participants who smoke or use tobacco products to stay awake) or a need for a cigarette within 30 minutes of waking in the morning.
26. Does not agree to follow the smoking restrictions as defined by the CRU.
27. Unable to refrain from alcohol intake from the EDS SOC washout period through Part 1 and Part 2 and until reinitiation of EDS SOC after completion of all study procedures in the last treatment period of Part 2 or until return to baseline at the discretion of the investigator.
28. Participant is, in the opinion of the investigator, at risk for alcohol withdrawal.
29. Consumes greater than 3 servings (1 serving is approximately equivalent to 120 mg of caffeine) of coffee, tea, cola, energy drinks, or other caffeinated beverages per day.
30. A POCBP who has a positive urine pregnancy test within 24 hours before first dose of study intervention (see Appendix 5). If the urine test cannot be confirmed as negative, a serum pregnancy test is required. In such cases, the participant must be excluded from participation if the serum pregnancy result is positive.
31. Is or has an immediate family member (eg, spouse, parent/legal guardian, sibling, or child) who is investigational site or Sponsor staff directly involved with this study.

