8.3.4.1 Resting Vital Signs

Vital Sign Measurements (Heart Rate and Blood Pressure)

Participants should be resting in a quiet setting without distractions for at least 10 minutes before having VS measurements obtained. VS will include HR, systolic and diastolic BP, RR, and body temperature at timepoints indicated in the SoA. The correct size of the BP cuff and the correct positioning on the participant's arm is essential to increase the accuracy of BP measurements.

At screening, HR and BP will be in triplicate measurements, obtained at least 1 minute apart (all 3 sets completed within 6 minutes). The median of the three measurements will be used to assess for participants eligibility.

Part 1

In each treatment period, the predose (baseline) HR and BP will be in triplicate measurements, obtained at least 1 minute apart (all 3 sets completed within 6 minutes) within 3 hours of dosing MK-6552. The median of these measurements will be used as the baseline to calculate change from baseline for safety evaluations (and for rechecks, if needed). Postdose VS measurements will also be measured in triplicate measurements.

Part 2

In each treatment period, on Days 1 and 7, the predose (baseline) HR and BP will be in triplicate measurements, obtained at least 1 minute apart (all 3 sets completed within 6 minutes) within 3 hours of dosing MK-6552/placebo. The median of these measurements will be used as the baseline to calculate change from baseline for safety evaluations (and for rechecks, if needed). All postdose VS measurements will be single measurements.

Poststudy visit HR and BP will be in triplicate measurements, obtained at least 1 minute apart (all 3 sets completed within 6 minutes).

Participants will continue to rest from dosing until 1 hour postdose except to stand for the measurement of orthostatic VS (if needed) or other study-related procedure.

Body Temperature

Body temperature will be measured in Part 1 only. The same method must be used for all measurements for each individual participant and should be the same for all participants at a given site.

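### Exclusion 1 joins its two blood pressure limits with 'and', so a participant at or above only one of them meets no numeric blood pressure exclusion

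*Combined protocol and SAP*

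**What the plan says.** Section 5.2 opens with "An individual must be excluded from the study if the individual meets any of the following criteria", so each item acts on its own, and an item that is not met excludes nobody. Exclusion 1 reads "History of or current hypertension defined as a SBP ≥ 140 mm Hg and a DBP ≥ 90 mm Hg". Exclusion 2 follows: "Has underlying cardiovascular or cerebrovascular conditions in which an acute rise in blood pressure would pose a clinical concern", with vascular lesions given as examples.

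Section 8.3.4.1 has heart rate and blood pressure taken in triplicate at screening and adds "The median of the three measurements will be used to assess for participants eligibility". It gives no cut-off, so the threshold has to come from section 5.

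Two further items rest on judgement. Inclusion 4 requires that the person "Is free of any disease that in the opinion of the investigator would interfere with trial evaluations based on medical history" and on examinations, vital signs and ECG; it allows an abnormal vital sign to be repeated once. Exclusion 18 removes anyone who, in the investigator's opinion, "has a history or current evidence of any condition, therapy, lab abnormality or other circumstances that might confound the results of the study". Neither gives a blood pressure figure. Appendix 8 sets screening limits for ECG findings only. Section 5 also states "Prospective approval of protocol deviations to recruitment and enrollment criteria, also known as protocol waivers or exemptions, is not permitted".

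**The concern.** The two limits are joined so that a single raised pressure, systolic or diastolic, falls outside the definition. The same holds for a history of hypertension if that history rests on one raised pressure only. Yet the next item in the list shows that the sponsor had an acute blood pressure rise in mind when writing the entry criteria.

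The study is the first use of the drug in people with narcolepsy type 1. Part 1 takes participants through four open-label periods, with vital signs feeding each escalation decision (section 6.6). If someone at or above one of the stated limits was meant to stay out, the text does not secure that. Whether the person enters then depends on the judgement of each site in a multisite study. The rule against waivers does not help: it stops a site admitting someone who meets an exclusion, but this person does not meet it.

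**Working it through.** **Step 1: logic of the criterion.** Let S mean SBP ≥ 140 mm Hg and D mean DBP ≥ 90 mm Hg, both on the screening median. The readings are illustrative.

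| Reading | S | D | Met as written (S and D) | Met under 'or' |
|---|---|---|---|---|
| 150/95 | yes | yes | yes | yes |
| 150/80 | yes | no | no | yes |
| 130/95 | no | yes | no | yes |
| 130/80 | no | no | no | no |

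The two readings differ only for people with exactly one raised pressure.

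**Step 2: does another item close the gap?**

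| Place | Blood pressure figure? | What triggers it |
|---|---|---|
| Exclusion 2 | none | an underlying cardiovascular or cerebrovascular condition |
| Inclusion 4 | none | investigator opinion, with vital signs as an input |
| Exclusion 18 | none | investigator opinion |
| Section 8.3.4.1 | none | says which value counts, not the limit |
| Appendix 8 | none | ECG findings |

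Exclusion 1 is therefore the only visible numeric blood pressure limit at entry.

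**Step 3: illustrative size.** The plan gives no figure to reproduce and no screening blood pressure data, so every input here is an assumption: SBP mean 120 or 130 and SD 12 or 15; DBP mean 77 or 82 and SD 9 or 10; correlation r of 0.5 or 0.7; bivariate normal. All 32 combinations were run.

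Formulas: a = (140 − SBP mean)/SBP SD; b = (90 − DBP mean)/DBP SD; P(both) = P(Z1 ≥ a, Z2 ≥ b); P(either) = P(Z1 ≥ a) + P(Z2 ≥ b) − P(both). The share of people at or above at least one limit who do not meet exclusion 1 is 1 − P(both)/P(either). Their share of the whole group is P(either) − P(both).

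- Smallest share: means 130/82, SDs 15/10, r = 0.7. Here a = 10/15 = 0.667 and b = 8/10 = 0.800. P(both) = 0.136 and P(either) = 0.252 + 0.212 − 0.136 = 0.329 before rounding of the parts. Share = 1 − 0.1355/0.3288 = 0.59.
- Largest share: means 120/82, SDs 12/10, r = 0.5. Here a = 20/12 = 1.667 and b = 0.800. P(both) = 0.029 and P(either) = 0.048 + 0.212 − 0.029 = 0.231. Share = 1 − 0.0290/0.2307 = 0.87.
- Smallest fraction of the whole group: means 120/77, SDs 12/9, r = 0.7. 0.098 − 0.024 = 0.074.
- Largest fraction of the whole group: means 130/82, SDs 15/10, r = 0.5. 0.357 − 0.107 = 0.250.

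Across all combinations P(either) runs from 0.098 to 0.357 and P(both) from 0.015 to 0.136. Extreme one-sided readings are rare in the same model: SBP ≥ 160 with DBP < 90 has probability at most 0.014, and SBP ≥ 170 with DBP < 90 at most 0.002.

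**The case against.** The strongest reply is that such people are not simply waved in. Inclusion 4 makes vital signs an input to eligibility independently of exclusion 1, exclusion 18 is broad, and section 8.1.2 has a qualified physician review every criterion. That stands: an investigator may well decline a markedly raised single pressure. But these routes depend on judgement and carry no blood pressure number, so they allow exclusion without requiring it.

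Second, exclusion 2 concerns people with underlying conditions. A reader might infer that it contradicts exclusion 1, or proves that 'or' was intended. It does neither. It shows why blood pressure matters in this study, and no visible text says which connector was meant.

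Third, a reader might infer that admitting these people will produce extra stopping-rule hits, or blood pressure findings that reflect baseline disease rather than dose. The documents do not support the first: the individual stopping criteria in section 7.1.1 and study stopping rules 4 to 6 in section 6.6.1 are redacted, so it is unknown whether a blood pressure rule exists or how it is framed. The second is weakened by section 8.3.4.1, which takes a fresh predose triplicate as baseline in each period, and by section 6.6, which reviews escalation participant by participant. Part 1 participants are also domiciled. These controls act after enrolment, so they soften the consequence and leave the entry wording as it is.

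Fourth, the percentages come from assumed distributions. Any comparison of 'and' with 'or' for two moderately correlated measures gives a large share, and most of the affected people would sit near the limits. Both remarks are right.

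**Conclusion.** The point holds as a wording gap in an entry criterion. As written, exclusion 1 does not reach a person at or above only one of the sponsor's two limits, and no other visible numeric limit does. This follows from the text alone and needs no assumption.

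The size is illustrative only. Under the assumed distributions, 59%-87% of people at or above at least one limit, or 7%-25% of an unselected group, would not meet exclusion 1. The fraction among those enrolled should be lower, because investigators can decline people and the study takes ages 18 to 55 with other medical exclusions. It cannot be estimated from the documents. Nor do the documents show that 'and' is a mistake; they leave the intent unstated. Because the item bears on participant safety and is cheap to settle, it should be settled in the protocol and not left to each site.

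**What to change.** The sponsor should state whether exclusion 1 requires both pressures or either one to reach its limit, and reconcile the connector with that intent and with the concern named in exclusion 2. If a reading at or above either stated limit is meant to exclude, 'and' must read 'or', with both thresholds left as they are and the rule applied to the median of the screening triplicate already collected under section 8.3.4.1. If both are required on purpose, a sentence saying so would remove the ambiguity.

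The change is one word or one sentence in an amendment. It needs no new procedure. If 'or' is adopted, there may be a few more screen failures.
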